Subjects will be randomized 1:1 to either active or sham RS-tDCS. The active RS-tDCS delivers a constant current intensity of 2mA on the subject's scalp, with SNAPstrap headgear and 5x7 (35cm2) SNAPpads positioning bilaterally (anodal-left and cathodal-right), on the DLPFC, for 30 minutes. A similar protocol's administration was found effective, safe, and tolerable as an add-on intervention to decrease depressive symptoms in patients with bipolar depression (45). Sham tDCS looks identical to a typical RS-tDCS cap but delivers a 30-second ramp-up (0-2 mA) stimulation followed by a 30-second rampdown (2-0 mA) at the beginning and end of the application. Figure 2 shows a representation of the electric current delivered by the active and sham RS-tDCS.

[figure not shown]

Figure 2. Stimulation protocol. Active tDCS (upper) and sham tDCS (lower).

The tolerability and safety of home-based tDCS were assessed over 6,779 sessions from six clinical trials. Sessions were administered daily, with treatment ranging from 10 to 60 sessions per subject. The authors reported no serious adverse events, a similar proportion of tingling (68%), itching (41%), and warmth sensation (42%) between active and sham groups, and no participant discontinuation due to lack of tolerability (39).

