8. STUDY PROCEDURES

The pre-screening will be carried out through the electronic hospital medical record to identify potential subjects. Once the potential subject is identified, research staff will visit the unit where the patient is receiving treatment (inpatient unit or CPEP) and talk with unit staff in person, providing information about the study. Then, the research staff will ask unit staff to determine the most appropriate time for the research staff to meet with the patient based on knowledge of patient status and needs.

[figure not shown]
After screening and signing consent, the research study staff will collect demographic and general medical history data, apply the clinical questionnaires, and conduct the orientation tDCS session as part of the in-person baseline assessment (Table 1 and Figure 3). This demographic, general medical history, and clinical data will be collected and stored in the REDCap through a tablet or another portable electronic device. Per subject need/request, research study staff reads aloud instructions and questions while subjects hold the tablet to record their answers. If the REDCap site is down or malfunctioning, screening, consent, and questionnaires are completed on paper and later entered into REDCap.

The orientation session includes presenting the Soterix Medical mini-CT device to the subject to show how to turn it on/off, how to insert the device unlock codes for one-time use, how to correctly adjust the SNAPstrap headgear, and answer any questions they may have. As part of the orientation session, research staff will also conduct a 90-s tolerability test, with 2.0 mA as the starting point (electrical current intensity of the study protocol). During this test, the current intensity is ramped up to 2.0 mA and the subject will receive the stimulation for 90 seconds. The tolerability will be determined by subject rating below 7 on the 0-10 Visual Analogue Scale (VAS) of pain. If the subject finds the target tDCS dose intolerable (i.e., VAS 7 or higher), subjects will have the option of another test, with the amperage dose decreased by 0.5 mA (i.e., to 1.5 mA). If this lower amperage is also intolerable, the subject will be excluded from the study (39, 46). Thus, the orientation session aims to 1) familiarize the subject with the

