device, how to turn it on/off, and insert the unlock codes for one-time use; 2) to assess if the subject tolerates the protocol electric current through the tolerability test; 3) answer any questions the subjects may have. As the Soterix Medical mini-CT device will be with the subjects during the RS-tDCS sessions, subjects will be asked to sign an IRB-approved device loan agreement at the baseline.

Clinical questionnaires will be re-administered at day 14 [+ 7 days], day 30 [+ 7 days], and day 60 [+ 10 days] from the first RS-tDCS session session15 (Figure 3). While we aim to reach subjects on the phone for follow-up, research staff may email or text subjects to schedule the RS-tDCS sessions and clinical assessments. Subject identifying information and protected health information (PHI) is not exchanged in the text messages themselves. Detailed information about text messaging is included under the "Privacy and Confidentiality of Subjects and Research Data" section. Security risks associated with text messaging are described in detail during consent.

After baseline assessment, research staff not involved in the RS-tDCS supervisions and clinical assessments will randomize the subject to active or sham control group and set up the device condition (active or sham), program the intensity for the active condition (either 2.0 mA or 1.5 mA, according to the tolerability test) and duration (30 minutes) of each session, and get the device unlock codes for one-time use to be provided by the research staff to the subject immediately before each session. The discharge day will be tracked daily by the research staff through the electronic hospital medical record. Once the subject is discharged, research staff will deliver the RS-tDCS device by mail to the subject's address in a pre-paid FedEx package to send it back and contact the subject once the device has arrived at their home (by using the mail tracking number) to schedule the first RS-tDCS session.

*device set up for the condition (active or sham), and locked (unlock codes for one-time use will be provided before each session); **day 1 being the first RS-tDCS session and no sessions on weekends. CPEP: Comprehensive Psychiatric Emergency Program; DLPFC: dorsolateral prefrontal cortex; RS-tDCS: remotely supervised transcranial direct current stimulation.

RS-tDCS sessions:

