The tolerability and safety of home-based tDCS were assessed over 6,779 sessions from six clinical trials, with daily session, varying from 10 to 60 applications. The authors reported no serious adverse events, a similar proportion of tingling (68%), itching (41%), and warmth sensation (42%) between active and sham groups, and no participant discontinuation due to lack of tolerability (39). As described in "Study procedures," a tolerability test will be performed as part of the orientation session to verify if the subject can tolerate the electric current established in the protocol. Subjects will be informed that they can stop an RS-tDCS session anytime. During the RS-tDCS session, the stimulation will be stopped if the subject reports a sensation of pain rated as an intensity of 7 or above on a 1-10 scale (46). If the subject reports any event of critical concern related since the last RS-tDCS session, the next RS-tDCS session will not start until clear that the event is not stimulation-related. All devices function only after the inclusion of a unlock code for one-time use. The unlock codes for one-time use allow the device to function only once a day, just after the inclusion of the code, with the level of electric current and duration of the session determined by the protocol, both (electric current level and duration of the session) pre-programmed on the device before it is delivered to the subject.

Imminent risk of suicide, for the purposes of this study, refers to a subject who is currently 1) thinking about suicide; 2) preparing for suicide and/or having planned for suicide; and has 3) some intent to act on the suicide plan within the very near future (generally 48 hours).

This may differ for each case and therefore, clinical judgment along with timely consultation are needed for determination of imminence. Thus, to assess imminent risk of suicide, the following procedures will be undertaken:

a) at the baseline assessment in the hospital:

- after the C-SSRS assessment, research staff will ask the subject if there is current active suicidal ideation with plan and intent. If the subject reports current active suicidal ideation plan and intent at the baseline, research staff will inform the subject that they need to communicate this information (about the active suicidal ideation with specific plan and intent) to the unit staff in charge of the patient due to safety concerns.

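### The tolerability test can lower the current in the active arm, but the only sham profile described peaks at 2 mA, so the two arms are not reconciled for subjects who qualify at 1.5 mA

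*Combined protocol and SAP*

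**What the plan says.** Section 4.1 (Study Intervention) states one current for each arm. For active: "The active RS-tDCS delivers a constant current intensity of 2mA on the subject's scalp". For sham, the device "delivers a 30-second ramp-up (0-2 mA) stimulation followed by a 30-second rampdown (2-0 mA) at the beginning and end of the application". It mentions no lower-current variant for either arm.

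Section 8 (Study Procedures) describes a test at the in-person orientation session, in which "the current intensity is ramped up to 2.0 mA and the subject will receive the stimulation for 90 seconds". Failing it does not end participation: "If the subject finds the target tDCS dose intolerable (i.e., VAS 7 or higher), subjects will have the option of another test", this time at 1.5 mA. Exclusion follows only if the lower level is not tolerated either. Randomization comes after this baseline visit. Staff outside the supervision and assessment team then set the device to active or sham and "program the intensity for the active condition (either 2.0 mA or 1.5 mA, according to the tolerability test". No setting is named for sham.

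Section 9 (Risks to Subjects) adds a stop during sessions: "the stimulation will be stopped if the subject reports a sensation of pain rated as an intensity of 7 or above".

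**The concern.** A subject can enter the trial having rated 2.0 mA at 7 or higher and having tolerated only 1.5 mA. Because allocation comes later, that subject can go to either arm. For active, section 8 provides a lower setting. For sham, the only profile in the protocol ramps to 2 mA at the start and end of each session. Staff who follow the text would therefore have a lower peak for the active subject and none for the sham subject.

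The direct stake is comfort and safety: the control arm could meet, briefly, a level that the trial's own test classed as intolerable for that person. The secondary stake is comparability. In this subgroup the peak current could be 1.5 mA in active and 2 mA in sham. Peak sensation, and with it side-effect scores, could then differ because of device set-up and not because of treatment. Blinding guesses and session completion could in principle be touched too.

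**Working it through.** The documents give no calculated figure on this point, so there is none to reproduce. The check is a comparison of the text, followed by simple arithmetic on exposure and on how many subjects might be affected.

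**Comparing the sections**

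| Step | Active | Sham |
|---|---|---|
| Section 4.1, general description | constant 2 mA | ramps 0-2 and 2-0 mA |
| Section 8, subject tolerates 2.0 mA | 2.0 mA | not stated; section 4.1 profile fits |
| Section 8, subject tolerates only 1.5 mA | 1.5 mA | not stated; section 4.1 profile peaks above the tolerated level |

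Two other places might have closed the gap but do not. The session description in section 8 says that current and duration are programmed in advance as the protocol determines, which for sham leads back to section 4.1. Section 13 (Subject Withdrawals) removes subjects who fail the tolerability test but refers back to section 8, so the retest at 1.5 mA stands. Figure 2, which depicts the two current profiles, is not in the text available here, and nothing is inferred from it.

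**Exposure of one affected sham subject under the written profile**

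Inputs: 30 s per ramp, peak 2.0 mA, an up/down pair at the beginning and another at the end (section 4.1); tolerated level 1.5 mA and ten sessions (section 8). Assumption: the ramps are linear.

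- Peaks: 2 per session × 10 sessions = 20.
- Time above 1.5 mA per ramp: 30 × (2.0 − 1.5)/2.0 = 7.5 s.
- Per up/down pair: 2 × 7.5 = 15 s. Per session: 2 × 15 = 30 s. Over ten sessions: 300 s.
- The text describes no hold at 2 mA in sham, so the peak is momentary. The tolerability test holds 2.0 mA for 90 s.

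**How many subjects**

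Inputs: 20 subjects (section 17) randomized 1:1 (section 4.1), so about 10 in sham. The proportion q who qualify only at 1.5 mA is not given. Expected number in sham = 10q; chance of at least one = 1 − (1 − q)^10.

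| Assumed q | Expected in sham | Chance of at least one |
|---|---|---|
| 0% | 0 | 0% |
| 5% | 0.5 | 1 − 0.95^10 = 40% |
| 10% | 1 | 1 − 0.90^10 = 65% |
| 20% | 2 | 1 − 0.80^10 = 89% |

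**Reach into the primary outcome**

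A subject counts towards feasibility with at least 5 of 10 sessions, so at least 10 − 4 = 6 sessions must be missed or uncompleted before one is lost. Each subject lost moves the pooled figure by 1/20 = 5 percentage points against the 70% rule.

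**The case against.** The strongest reply is that the protocol is silent on sham programming for these subjects. It does not order the sham device to stay at 2 mA. Section 8 may name only the active condition because sham has no sustained current to set, and sections 8 and 9 describe current as programmed on the device in advance without restricting that to active. This stands: actual set-up may differ from the written profile. A reader might infer that the protocol requires sham subjects to receive 2 mA regardless of their test result; the text does not go that far. It does, however, offer staff no other sham profile.

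The active half can also be defended. Section 8 treats 2.0 mA as the target and then makes an explicit exception, so section 4.1 can be read as the standard case. That is fair, and it leaves sham as the part that cannot be resolved by reading the sections together.

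A reader might also infer that affected sham subjects repeat the exposure they failed. They would not: a momentary peak is not 90 s at 2.0 mA, and a rating of 7 or higher during a ramp is possible, not certain. Sessions are supervised by video, the subject may stop at any time, and section 9 stops stimulation at a pain rating of 7.

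Finally, the rate is unanchored. The tolerability evidence the protocol cites reports no participant discontinuation for lack of tolerability in 6,779 home sessions. That is not the same as the rate of failing 2.0 mA on this test, but it means that a rate near zero cannot be set aside.

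**Conclusion.** The inconsistency is real and should be corrected. The tolerability rule admits subjects for whom the only written sham profile peaks at a level they rated intolerable, while the lower setting is written for active alone. This is more than a missing detail, because following the text gives the two arms different peak currents in this subgroup.

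Its size is modest. For each affected sham subject it is up to 20 brief peaks, or about 300 s above 1.5 mA over ten sessions, given linear ramps and a sham device left at the section 4.1 profile. The number affected depends on a rate the documents do not give: 0 to 2 of about 10 sham subjects over the assumed range of 0% to 20%.

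The documents do not support a claim that blinding is broken or that the feasibility result is biased. Nothing fixes the direction or size of any effect on treatment guesses. Losing one subject from the primary outcome requires failing 2.0 mA, accepting and passing the retest, allocation to sham, a sham device left at 2 mA, and then at least six sessions not completed. The 5-point shift applies only at the end of that chain, to which no probability can be attached. Both effects remain possible but unquantified. No view is taken on which current is right in either arm.

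**What to change.** Reconcile section 4.1 with the orientation-session and device-programming text in section 8. One statement should say how the tolerability-test result sets the programmed current profile in both the active and the sham arm, for subjects who qualify at either level. Give the staff member who programs the devices the matching instruction, and record the tolerated level for each subject.

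Separate reporting of feasibility or blinding guesses by tolerated level is not worth adding: at 5% to 20% of 20 subjects the subgroup would hold about 1 to 4 people and could not be interpreted.

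The cost is a protocol wording change, one programming instruction for staff who already set each device outside the supervision and assessment team, and one recorded data item. Sample size, visits and analysis are unchanged.

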5. INCLUSION AND EXCLUSION CRITERIA

Inclusion criteria:

- age between 18 and 65 years

- diagnosis of mood or bipolar disorder registered in the electronic hospital medical record

- history of suicidal ideation and/or suicide behavior at the time of admission registered in the electronic hospital medical record

- absent of suicidal ideation at the time of enrollment (defined as questions 1 and 2 of the C-SSRS answered "no").

- ability and willingness to provide information and permission to contact at least one person in the case of a need to contact them to promote subject safety or inability to reach the subject for follow-up

- a living situation with access to a private space suitable for administration of the RS-tDCS sessions in next three weeks

- agree to use a medically acceptable form of birth control while receiving the treatment if you are an individual able to become pregnant

- living in Monroe County region, as this is the area covered by the Mobile Crisis Team, a URMC psychiatric emergency team serving anyone within Monroe County

- device or computer with internet access for a URMC-approved remote RS-tDCS supervision

- ability to manage proper use of the device in a practice session

Exclusion criteria:

- acute psychiatric instability or substance abuse (e.g., psychotic symptoms, alcohol misuse in the previous three months, use of any illicit drugs in the previous three months)

- unstable medical condition with reduction of functional capacity

- history of epilepsy or seizures in the last year

- history of neurodegenerative diseases registered in the electronic hospital medical record
- presence of or implanted any ferromagnetic metal in the head or the neck
- pregnant or breastfeeding or willingness to become pregnant in the next month

- history of head trauma (e.g., head injury, brain injury) or neurosurgery
- history of skin disorder or sensitive skin area near stimulation locations
- the presence of pacemaker
- current treatment with electroconvulsive therapy or transcranial magnetic stimulation

Although concurrent treatment with medications or psychotherapy is not an exclusion criterion, we will measure changes in medication and psychotherapy for descriptive and planning purposes (please, see "Secondary outcome measures", item 9).

6. RECRUITMENT METHODS

We will recruit potential subjects (i.e., those with a history of suicidal ideation and/or suicidal behavior at the time of admission registered in the electronic hospital medical records) from inpatient units and the Comprehensive Psychiatric Emergency Program (CPEP) of the URMC. After pre-screening the electronic hospital medical record to identify potential subjects, research staff will contact unit staff in-person, providing information about the study. Then, the research staff will ask unit staff to determine the most appropriate time for research staff to meet with the patient based on knowledge of the patient status and needs.

Research staff assess eligibility using standardized questions and enter potential subjects' answers on a dedicated REDCap form. Eligibility data are retained for regular reporting and PI oversight. If there is interest in participation, research staff asks permission to collect their name and phone number on the contact information form. This identifiable information is marked with REDCap's "identifier" designation, which allows it to be automatically removed in data exports. This individual form is only accessible to staff who need to contact the subjects. This precautionary measure is described to potential subjects at the interview's beginning. Those who are eligible and interested undergo the informed consent process described below (see Consent Process).

7. CONSENT PROCESS

Informed consent will be obtained using the institutional review board (IRB)-approved form inperson, in a private setting, and through a paper copy.

Inform consent process includes a detailed description of the study procedures, and statements regarding subjects' rights to withdraw from the procedure at any time without consequences. It is explained to subjects in easy-to-understand language. Consent is documented by the subject's signature on the consent form, accompanied by the signature of a research team member. During consent and throughout the study, it is emphasized that participation or non-participation in the study does not affect the patient's treatment at the hospital. Likewise, they are advised to withdraw their participation in the study at any time. The limits of confidentiality are also explained, including the potential to break confidentiality in the event of acute risk of suicidal behavior or violence or disclosures of unreported physical or sexual abuse of a child.

Consent includes an authorization for staff to access subjects' electronic hospital medical records. Research staff collects information from records related to admission and discharge dates, suicidal ideation, method and circumstance of self-harming behavior, diagnoses, and medication.

Subjects who consent to research participation are given a full research assessment battery. Those who do not consent to participate in the research study return to receiving routine

care provided by the referring clinical service.

To minimize the possibility of coercion or undue influence, the consent process is carried out by research staff employed for the study and will not involve any members of the patient's treatment scheme. Patients are encouraged to ask questions about participation in the study. They may take as much time as necessary to consider participation and consult with family members or the treatment team. Patients are reminded that participation is voluntary, and they may withdraw from the study anytime.

Once the consent form is signed, subjects will receive a printout of the paper copy signed consent form. The PI and the Co-PI of the study will be responsible for maintaining all approved pages of the signed consent forms for at least 6 years after the research is completed and the Research Subjects Review Board (RSRB) file is closed, or for a longer term if required by FDA regulations or other contractual agreements. A link will be maintained between the consent document and subject number in order to be able to link signed consent documents to study data. In addition, we will keep a blank approved copy of all RSRB approved consent documents at the time of every approval. The signed consent forms will be stored in chronological order in a locked cabinet in the Co-PI's office. If the PI leaves the institution, the original signed consents will remain at the University of Rochester. Certificate of Confidentiality: as an added protection, the study is covered by a Federal Certificate of Confidentiality from the Department of Health and Human Services (DHHS). The appropriate language is included in the consent form.

8. STUDY PROCEDURES

The pre-screening will be carried out through the electronic hospital medical record to identify potential subjects. Once the potential subject is identified, research staff will visit the unit where the patient is receiving treatment (inpatient unit or CPEP) and talk with unit staff in person, providing information about the study. Then, the research staff will ask unit staff to determine the most appropriate time for the research staff to meet with the patient based on knowledge of patient status and needs.

[figure not shown]
After screening and signing consent, the research study staff will collect demographic and general medical history data, apply the clinical questionnaires, and conduct the orientation tDCS session as part of the in-person baseline assessment (Table 1 and Figure 3). This demographic, general medical history, and clinical data will be collected and stored in the REDCap through a tablet or another portable electronic device. Per subject need/request, research study staff reads aloud instructions and questions while subjects hold the tablet to record their answers. If the REDCap site is down or malfunctioning, screening, consent, and questionnaires are completed on paper and later entered into REDCap.

The orientation session includes presenting the Soterix Medical mini-CT device to the subject to show how to turn it on/off, how to insert the device unlock codes for one-time use, how to correctly adjust the SNAPstrap headgear, and answer any questions they may have. As part of the orientation session, research staff will also conduct a 90-s tolerability test, with 2.0 mA as the starting point (electrical current intensity of the study protocol). During this test, the current intensity is ramped up to 2.0 mA and the subject will receive the stimulation for 90 seconds. The tolerability will be determined by subject rating below 7 on the 0-10 Visual Analogue Scale (VAS) of pain. If the subject finds the target tDCS dose intolerable (i.e., VAS 7 or higher), subjects will have the option of another test, with the amperage dose decreased by 0.5 mA (i.e., to 1.5 mA). If this lower amperage is also intolerable, the subject will be excluded from the study (39, 46). Thus, the orientation session aims to 1) familiarize the subject with the

device, how to turn it on/off, and insert the unlock codes for one-time use; 2) to assess if the subject tolerates the protocol electric current through the tolerability test; 3) answer any questions the subjects may have. As the Soterix Medical mini-CT device will be with the subjects during the RS-tDCS sessions, subjects will be asked to sign an IRB-approved device loan agreement at the baseline.

Clinical questionnaires will be re-administered at day 14 [+ 7 days], day 30 [+ 7 days], and day 60 [+ 10 days] from the first RS-tDCS session session15 (Figure 3). While we aim to reach subjects on the phone for follow-up, research staff may email or text subjects to schedule the RS-tDCS sessions and clinical assessments. Subject identifying information and protected health information (PHI) is not exchanged in the text messages themselves. Detailed information about text messaging is included under the "Privacy and Confidentiality of Subjects and Research Data" section. Security risks associated with text messaging are described in detail during consent.

After baseline assessment, research staff not involved in the RS-tDCS supervisions and clinical assessments will randomize the subject to active or sham control group and set up the device condition (active or sham), program the intensity for the active condition (either 2.0 mA or 1.5 mA, according to the tolerability test) and duration (30 minutes) of each session, and get the device unlock codes for one-time use to be provided by the research staff to the subject immediately before each session. The discharge day will be tracked daily by the research staff through the electronic hospital medical record. Once the subject is discharged, research staff will deliver the RS-tDCS device by mail to the subject's address in a pre-paid FedEx package to send it back and contact the subject once the device has arrived at their home (by using the mail tracking number) to schedule the first RS-tDCS session.

*device set up for the condition (active or sham), and locked (unlock codes for one-time use will be provided before each session); **day 1 being the first RS-tDCS session and no sessions on weekends. CPEP: Comprehensive Psychiatric Emergency Program; DLPFC: dorsolateral prefrontal cortex; RS-tDCS: remotely supervised transcranial direct current stimulation.

RS-tDCS sessions:

Research staff with training in using home-based tDCS by the Soterix Medical will meet with the subject via HIPAA-compliant videoconference previously scheduled. Subjects will be encouraged to find a distraction-free setting to complete treatment sessions. After guiding the subject with the proper adjustment of the SNAPstrap headgear and turning on the 1 x 1 Mini-CT device, research staff will provide the device unlock codes for one-time use to the subject. All ten device unlock codes for one-time use (one for each tDCS session) are obtained previously, just after the device is programmed to active or sham. The device unlock codes for one-time use allow the device to function only once a day, just after the inclusion of the code, with the level of electric current and duration of the session determined by the protocol, both (electric current level and duration of the session) pre-programmed on the device before it is delivered to the subject. Thus, the subject cannot alter the electric current level, the duration of the session, or use the device more than once a day. After each RS-tDCS session, research staff will apply the side effects questionnaire, review the subject's current treatment ("treatment review"), ask about any new or updated mental or physical symptoms since the last assessment (adverse events review), and apply the C-SSRS - screening version (C-SSRS SV) as part of the risk assessment (please, see more details on item "9. RISK TO SUBJECTS"). After the last RS-tDCS session (the tenth session), research staff will apply the feasibility questionnaire and blinding assessment. (Table 1). To assess blinding, the subjects will be asked the following question, "What treatment do you believe you have received??"(47). There will be three possible answers: 1) "active-tDCS"; 2)

"sham-tDCS" or 3) "Don't know". If the answer is "Don't know", research staff will ask "Would you be willing to provide your best guess about the treatment you received?", and could choose from two possible replies: 1) active-tDCS; 2) sham-tDCS (47, 48). We will use the Bang Blinding Index, which varies from -1 to +1, being 1 complete lack of blinding, +1 the opposite guessing, and 0 being related to perfect blinding (48). After the tenth session, the subject will be asked to send back the equipment in the pre-paid mail package to send it back.

Clinical assessments:

Clinical assessments with be performed at day 14 [+ 7 days], day 30 [+ 7 days], and day 60 [+ 10 days] from the first RS-tDCS session with the questionnaires described in Table 1. Thus, the duration of and individual's participation in the study will be up to 70 days.

